5.1. Summary of Study Design

Study RHBH is a Phase 3, multicenter, randomized, double-blind, placebo-controlled, parallel-group, outpatient study examining the effect of ixekizumab versus placebo in patients with moderate-to-severe plaque Ps during an Induction Dosing Period with the primary endpoint at 12 weeks, followed by a re-randomized Maintenance Dosing Period to Week 60. During the Induction Dosing Period, the study will evaluate the efficacy and safety of 2 dose regimens of ixekizumab (80 mg Q2W or Q4W). During the Maintenance Dosing Period, the study will evaluate the maintenance of response/remission with the dose regimen of 80 mg Q4W ixekizumab, the safety of the regimen, as well as relapse or rebound following treatment withdrawal, and response to retreatment following relapse.

The study consists of 4 periods:

- **Period 1: Screening Period** (Visit 1 and Visit 1A) lasting from 4 to 30 days prior to Period 2 (baseline; Week 0; Visit 2).
- **Period 2: Induction Dosing Period** will be a double-blind treatment period that will occur from Week 0 (baseline; Visit 2) to Week 12 (Visit 7).
- **Period 3: Maintenance Dosing Period** will be a double-blind treatment period that will occur from Week 12 (Visit 7) to Week 60 (Visit 19).
- **Period 4: Post-Treatment Follow-Up Period** occurring from last treatment period visit or Early Termination Visit (ETV) up to a minimum of 12 weeks following that visit.

Figure RHBH. 5.1. illustrates the study design.

[figure not shown]

Figure RHBH. 5.1. Illustration of study design for Clinical Protocol I1F-MC-RHBH.

Illustration of study design for Clinical Protocol I1F-MC-RHBH (not to scale) (Abbreviations and footnotes)

Abbreviations: LV = date of last visit; LY = ixekizumab (LY2439821); n = number of patients; Pbo = placebo; Q2W = every 2 weeks; Q4W = every 4 weeks; V = study visit; W = study week.

- a All patients will receive 2 SC doses of investigational product (ixekizumab 80 mg, placebo) starting at Week 0 (Visit 2) and 1 SC dose Q2W from Week 2 (Visit 4) through Week 10.
- b All patients will receive 2 SC doses of investigational product (ixekizumab or placebo) at Week 12 (Visit 7) and 1 SC dose Q4W from Week 16 (Visit 8) through Week 56 (Week 60, no investigational product administration).
- c All patients receiving investigational product must enter into Period 4 and complete through Visit 802. Patients may be followed beyond Visit 802 for continued monitoring of their neutrophil count if needed, or if determined by the sponsor/investigator that additional monitoring is needed.
- d Responders to ixekizumab at Week 12 (Visit 7; responders are defined as achieving an sPGA score of 0 or 1) will be randomly assigned at a 2:1 ratio to ixekizumab Q4W or placebo.
- e Nonresponders to ixekizumab at Week 12 (Visit 7; nonresponders are defined as having an sPGA score of >1) will receive ixekizumab 80 mg Q4W.
- f Responders to placebo at Week 12 (Visit 7) will receive 2 injections of placebo at Week 12 and will remain on placebo Q4W until relapse, then they will be switched to 80 mg ixekizumab Q4W.
- g Nonresponders to placebo at Week 12 (Visit 7) will receive 2 injections of ixekizumab (starting dose) at Week 12 followed by ixekizumab 80 mg Q4W
- h Relapse (loss of response) occurring after Week 12 (Visit 7) is defined as an sPGA score of ≥ 3 .

5.2. Method of Assignment to Treatment

At Week 0 (Visit 2), patients who meet all criteria for enrollment at Visits 1/1A and 2 will be randomized at a 2:2:1 ratio to ixekizumab 80 mg Q2W, ixekizumab 80 mg Q4W, or placebo. Assignment to double-blind treatment groups will be determined by a computer-generated random sequence using an interactive web response system (IWRS). The IWRS will be used to assign double-blind investigational product to each patient. Site personnel will confirm that they have located the correct assigned investigational product package by entering a confirmation number found on the package into the IWRS.

At Week 12 (Visit 7), patients who enter Period 3 will be classified as a responder (sPGA score of 0 or 1) or non-responder (sPGA score of >1). Patients who received ixekizumab during Period 2 and who are responders will be re-randomized at a 2:1 ratio to 80 mg Q4W or placebo using the IWRS. Patients will be stratified by ixekizumab induction dosing regimen (80 mg Q2W or 80 mg Q4W). Patients who received placebo during Period 2 and who are responders will be assigned to continue to receive placebo until relapse occurs. Relapse (loss of response) is defined as an sPGA score of ≥ 3 . Non-responders who received any investigational product (assigned to any treatment group) during Period 2 will be assigned to receive treatment with 80 mg ixekizumab Q4W. Assignment to treatment will be determined by the IWRS.

5.3. Determination of Sample Size

The total sample size for the study is 420 patients randomized at a 2:2:1 ratio in the blinded Induction Dosing Period to 80 mg Q2W, 80 mg Q4W, and placebo, respectively. In order to account for multiple testing for the 2 ixekizumab groups, a 2-sided Fisher's exact test at the 0.025 level is assumed. Assuming the response rates for both sPGA (0,1) and PASI 75 at Week 12 (Visit 7) are 75% for each ixekizumab treatment group and 5% for the placebo group, 168 patients in 80 mg Q2W or 80 mg Q4W versus 84 patients in placebo group will provide >99% power to test the superiority of each ixekizumab dose regimen to placebo for sPGA (0,1) and for PASI 75. These assumptions are based on the integrated results from the pivotal Phase 3 Studies RHAZ, RHBA, and RHBC.

Assuming 70% of the ixekizumab patients are re-randomized in the Maintenance Dosing Period at Week 12 (Visit 7) at a 2:1 ratio to 80 mg Q4W or placebo, approximately 78 patients will be included in 80 mg Q4W group and 39 patients in placebo group. This sample size will:

- provide >99% power to test the difference in the proportion of patients maintaining sPGA (0, 1) from Week 12 (Visit 7) after re-randomization at start of Maintenance Dosing Period to Week 60 (Visit 19) in the Maintenance Dosing Period Primary population between the ixekizumab dosing interval and placebo within the original treatment group, assuming the proportions of patients maintaining sPGA (0, 1) are 70% for 80 mg Q4W and 10% for placebo within each original treatment group (Visit 19). A 2-sided Fisher's exact test at the 0.025 significance level is assumed.
- provide >99% power to test the difference in the proportion of patients maintaining a PASI 75 from Week 12 (Visit 7) after re-randomization at start of Maintenance Dosing Period to Week 60 (Visit 19) in the Maintenance Dosing Period Primary population

between the ixekizumab dosing interval and placebo within each original treatment group, assuming the proportions of patients maintaining a PASI 75 are 70% for 80 mg Q4W and 10% for placebo within each original treatment group. A 2-sided Fisher's exact test at the 0.025 significance level is assumed.

6. A Priori Statistical Methods

6.1. General Considerations

Statistical analysis of this study will be the responsibility of Eli Lilly and Company (hereafter Lilly). The statistical analyses will be performed using SAS® Version 9.2 or higher. The latest version of the Medical Dictionary for Regulatory Activities (MedDRA®) will be used.

Not all displays and analyses described in this SAP will necessarily be included in the CSR. Not all displays will necessarily be created as a “static” display. Some displays may be incorporated as interactive display tools such as Spotfire instead of or in addition to a static display. Any display described in this SAP and not provided in CSR would be available upon request.

Any change to the data analysis methods described in the protocol will require a protocol amendment ONLY if it changes a principal feature of the protocol. Any other change to the data analysis methods described in the protocol and the justification for making the change will be described in CSR.

6.1.1. Analysis Population

The following major analysis populations will be used (additional analysis populations for specific analysis will be defined in the corresponding analysis section):

Intent-to-Treat Population (ITT): Unless otherwise specified, efficacy and health outcomes analyses for Period 2 (Induction Dosing Period) will be conducted on the intent-to-treat (ITT) population, defined as all randomized patients, even if the patient does not take the assigned treatment, does not receive the correct treatment, or otherwise does not follow the protocol. Patients will be analyzed according to the treatment to which they are assigned.

Per Protocol Set (PPS): In addition, the primary analysis will be repeated using the per protocol set (PPS), which is defined as all randomized patients who are compliant with therapy, who do not have a subset of important protocol deviations that impact the primary efficacy endpoint (Section 6.5), and whose investigator site does not have significant good clinical practice (GCP) issues that require a report to the regulatory agencies prior to Week 12 (Visit 7). Compliance with therapy is defined to be missing no more than 20% of expected doses, not missing 2 consecutive doses, and no double dosing (that is, taking more injections at the same time point than specified in the protocol) during the period that patients participated in the study and prior to Week 12 (Visit 7) (see Section 6.8). Patients will be analyzed according to the treatment to which they are assigned.

Safety Population: Safety analyses for Period 2 will be conducted on the Safety Population, defined as all randomized patients who received at least 1 dose of study treatment. Patients will be analyzed according to the treatment to which they were assigned.

Maintenance Dosing Period Primary population: defined as all re-randomized patients (that is, patients randomized to ixekizumab in Period 2 who achieved an sPGA (0, 1) and were re-randomized at Week 12) who received at least 1 dose of study treatment during Period 3.

Patients will be analyzed according to the treatment to which they were re-randomized. Only information prior to relapse will be presented.

Maintenance Dosing Period Secondary population: defined as the ixekizumab patients who were not re-randomized at Week 12 or patients who were randomized to placebo at Week 0, who received at least 1 dose of study treatment during Period 3. Patients will be analyzed according to the treatment to which they were assigned upon entry into Period 3.

Maintenance Dosing Period Relapse population: defined as all patients who were responders at Week 12 (that is, patients who achieved an sPGA (0,1) at Week 12) who first experience a relapse (sPGA ≥ 3) at any point during the maintenance dosing period (that is, Period 3). Although all patients will receive 80 mg Q4W, patients will be analyzed according to the treatment to which they were re-randomized or assigned at Week 12 (see treatment groups defined in [Table RHBH. 6.1.](#)).

Follow-up Population: Safety analyses for Period 4 (Post-Treatment Follow-up Period) will be conducted on the follow-up population, defined as all randomized patients who received at least 1 dose of study treatment and have entered the post-treatment follow-up period. Patients will be analyzed according to the treatment they actually received prior to entering Period 4.

[Table RHBH. 6.1.](#) describes the treatment groups and the comparisons for each study period and the analysis population.

Table RHBH. 6.1. Treatment Groups and Comparisons for Each Study Period and Analysis Population

Study Period	Analysis Population	Treatment Group	Abbreviation	Comparison
Induction Dosing Period (Period 2)	Intent-to-Treat Population; Per Protocol Set; Safety Population	Placebo	PBO	IXE80Q4W vs. PBO; IXE80Q2W vs. PBO; Overall ^a
		Ixekizumab 80 mg Q4W	IXE80Q4W	
		Ixekizumab 80 mg Q2W	IXE80Q2W	
		Total Ixekizumab	Total IXE	
		Total	Total	
Maintenance Dosing Period (Period 3)	Maintenance Dosing Period Primary Population (by Individual Dose)	Ixekizumab 80 mg Q4W/Placebo	IXE80Q4W/PBO	IXE80Q4W/IXE80Q4W vs IXE80Q4W/PBO; IXE80Q2W/IXE80Q4W vs IXE80Q2W/PBO Overall ^a
		Ixekizumab 80 mg Q4W/Ixekizumab 80 mg Q4W	IXE80Q4W/IXE80Q4W	
		Ixekizumab 80 mg Q2W/Placebo	IXE80Q2W/PBO	
		Ixekizumab 80 mg Q2W/ Ixekizumab 80 mg Q4W	IXE80Q2W/IXE80Q4W	
		Total	Total	
	Maintenance Dosing Period Primary Population (by Pooled Dose)	Ixekizumab/Placebo	IXE/PBO	IXE/IXE vs IXE/PBO
		Ixekizumab/Ixekizumab	IXE/IXE	
		Total	Total	
	Maintenance Dosing Period Secondary Population ^b	PlaceboResp/Placebo	PBOResp/PBO	No Comparison
		PlaceboNonR/Ixekizumab 80 mg Q4W	PBONonR/IXE80Q4W	
		Ixekizumab 80 mg Q4WNonR/Ixekizumab 80 mg Q4W	IXE80Q4WNonR/IXE80Q4W	
		Ixekizumab 80 mg Q2WNonR/Ixekizumab 80 mg Q4W	IXE80Q2WNonR/IXE80Q4W	
		Total Ixekizumab	Total IXE	
	Maintenance Dosing Period Relapse Population	PlaceboResp/Placebo	PBOResp/PBO	No Comparison
		Ixekizumab 80 mg Q4W/Placebo	IXE80Q4W/PBO	
		Ixekizumab 80 mg Q4W/Ixekizumab 80 mg Q4W	IXE80Q4W/IXE80Q4W	
		Ixekizumab 80 mg Q2W/Placebo	IXE80Q2W/PBO	
		Ixekizumab 80 mg Q2W/Ixekizumab 80 mg Q4W	IXE80Q2W/IXE80Q4W	
		Total	Total	
Post-Treatment Follow-Up Period (Period 4) ^c	Follow-Up Population	Placebo	PBO	No Comparison
		Ixekizumab 80 mg Q4W	IXE80Q4W	
		Ixekizumab 80 mg Q2W	IXE80Q2W	
		Total Ixekizumab	Total IXE	
		Total	Total	

Abbreviations: IXE = ixekizumab; Q2W = every 2 weeks; Q4W = every 4 weeks; vs. = versus.

- a Overall comparison will be conducted for demographics, historical illness, medical history, preexisting condition, and previous therapy. The pairwise comparisons and the overall comparison will be conducted for concomitant therapy, compliance, disposition, and safety.
- b For maintenance dosing secondary population, 'Total IXE' is the pooled group of PBONonR/IXE80Q4W, IXE80Q4WNonR/IXE80Q4W and IXE80Q2WNonR/IXE80Q4W.
- c Treatment Group refers to the treatment regimen that the patient received prior to entering Period 4.

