  - Time course of response to treatment as measured by change from baseline and percent improvement from baseline of PASI
  - Change from baseline in percent of BSA involvement of Ps
  - Incidence of disease rebound within 8 weeks (worsening of Ps severity over baseline sPGA score, *or* worsening of Ps severity over baseline PASI score by 125%, *or* change in Ps phenotype [for example, from plaque to pustular]) after re-randomization to placebo at Week 12
  - Time course of response to treatment as measured by the proportion of patients who maintain a PASI 75, PASI 90, and PASI 100
  - Change from baseline in NAPSI score in patients with baseline fingernail involvement
  - Change from baseline in PSSI score in patients with baseline scalp involvement

- Change from baseline in other health outcome endpoints: SF-36 PCS and MCS scores and patient's global assessment of disease severity
- Change from baseline in itching severity (Itch NRS) score
- Change from baseline on DLQI
- Change from baseline in PPASI and proportion of patients achieving at least a 50% improvement in PPASI score from baseline (PPASI 50), at least a 75% improvement in PPASI score from baseline (PPASI 75), and a 100% improvement in PPASI score from baseline (PPASI 100) in patients with baseline palmoplantar involvement
- To assess the efficacy of ixekizumab 80 mg Q4W following disease relapse after re-randomization to placebo treatment in the Maintenance Dosing Period by evaluating:
  - Proportion of patients who regain an sPGA (0, 1) within 12 weeks after ixekizumab retreatment
  - Proportion of patients who achieve a PASI 75, PASI 90, PASI 100 within 12 weeks after ixekizumab retreatment
- To assess the efficacy of ixekizumab 80 mg Q2W or 80 mg Q4W compared to placebo on joint pain at Week 12 and over the Induction Dosing Period, as well as at Week 60 and during the Maintenance Dosing Period in patients with an sPGA (0, 1) at Week 12 and were re-randomized, by evaluating change from baseline in joint pain (Joint Pain visual analog scale [VAS]) score in patients with psoriatic arthritis (PsA) at baseline
- To evaluate the potential development of anti-ixekizumab antibodies and its impact on patient safety and efficacy
- To measure ixekizumab exposure and assess the relationship between exposure and efficacy, and exposure and immunogenicity

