- Patients receiving 80 mg ixekizumab Q4W, who relapse, will continue on 80 mg ixekizumab Q4W in order to maintain the study blind and to evaluate the long term efficacy of ixekizumab treatment.
- Patients receiving placebo who relapse will be switched to 80 mg ixekizumab Q4W.

Continued treatment for patients who relapse is provided to understand the longer-term efficacy of ixekizumab when treating patients who experience relapse and to maintain study blinding. See Section 8.3.1 for discontinuation criteria.

**Treatment Assignment for Non-Responders:** Patients randomized to ixekizumab at Week 0 (Period 2) who are non-responders at Week 12 (Visit 7) will receive treatment with 80 mg ixekizumab Q4W during Period 3.

Patients randomized to placebo at Week 0 (Period 2) who are non-responders at Week 12 (Visit 7) will receive treatment with 80 mg ixekizumab Q4W during Period 3. These patients will receive a starting dose of 160 mg ixekizumab as 2 SC injections at Week 12 (Visit 7).

Continued treatment for non-responders is provided so that partial or slow responders to ixekizumab and non-responders to placebo may remain in the study and receive treatment with ixekizumab while maintaining the study blind. Some patients may be deriving benefit from treatment with ixekizumab but will be slow responders or partial responders thereby not meeting the “responder” criteria at Week 12. A discontinuation criterion for patients who remain at or above their baseline sPGA score at both Week 12 and Week 24 is included (see Section 8.3.1) to ensure that patients who have not shown any benefit from treatment with ixekizumab can be treated with any other psoriasis therapy as determined appropriate by the investigator.

Once a patient has switched to 80 mg Q4W, regardless of original treatment in Period 2, re-randomization in Period 3, or any assessments of response/relapse, the patient will remain on 80 mg Q4W.

Patients who discontinue the study for any reason during Period 3 will stop treatment and continue to the ETV prior to entering the Post-Treatment Follow-Up Period (Period 4; Section 7.1.4).

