### 8.1. Inclusion Criteria

Patients are eligible to be included in the study only if they meet **all** of the following criteria:

[1] Are male or female patients 18 years or older

[1a] Male patients agree to use a reliable method of birth control during the study and for at least 12 weeks following the last dose of investigational product. Examples of reliable methods include abstinence, vasectomy, and male condom with spermicide.

[1b] Female patients:

Are women of childbearing potential who test negative for pregnancy and agree to use a reliable method of birth control or remain abstinent during the study and for at least 12 weeks following the last dose of investigational product, whichever is longer. Methods of contraception considered acceptable include oral contraceptives, contraceptive patch, intrauterine device, vaginal ring, diaphragm with contraceptive gel, or condom with contraceptive gel.

-or-

Are women of non-childbearing potential, defined as:

Women who have had surgical sterilization (hysterectomy, bilateral oophorectomy, or tubal ligation);

-or-

Women who are  $\geq 60$  years of age;

-or-

Women  $\geq 40$  and  $< 60$  years of age who have had a cessation of menses for  $\geq 12$  months and a follicle-stimulating hormone (FSH) test confirming non-childbearing potential ( $\geq 40$  mIU/mL)

- [2] Present with chronic plaque Ps based on a confirmed diagnosis of chronic Ps vulgaris for at least 6 months prior to baseline (Week 0; Visit 2)
- [3] Have  $\geq 10\%$  BSA involvement at screening (Visit 1) and baseline (Week 0; Visit 2)
- [4] Have both an sPGA score of  $\geq 3$  and PASI score  $\geq 12$  at screening (Visit 1) and baseline (Week 0; Visit 2)
- [5] Are candidate for phototherapy and/or systemic therapy
- [6] Have given written informed consent approved by Lilly, or its designee, and the Investigational Review Board (IRB)/ERB governing the site

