**Table RHBH.12.1. Treatment Comparisons during the Maintenance Dosing Period**

Induction Dosing	Maintenance Dosing	Treatment Group Comparisons during the Maintenance Dosing Period
80 mg Q2W = Dose 1	80 mg Q4W = Dose 1A Placebo = Dose 1B	Dose 1A versus Dose 1B
80 mg Q4W = Dose 2	80 mg Q4W = Dose 2A Placebo = Dose 2B	Dose 2A versus Dose 2B

Abbreviations: Q2W = once every 2 weeks; Q4W = once every 4 weeks.

For the efficacy and health outcomes analyses, baseline is defined as the last available value before the first injection in Period 2; in most cases it will be the value recorded at Week 0 (Visit 2).

Unless otherwise specified, for the Period 3 safety analyses, baseline and baseline period are defined as the last non-missing assessment prior to the first injection of study treatment at Week 12 (Visit 7). In most cases, this will be the measure recorded at Week 12 (Visit 7). For treatment-emergent adverse events, baseline value is the measure recorded at the last visit prior to the study drug injection at Week 12 (Visit 7).

Change from baseline will be calculated as the visit value of interest minus the baseline value.

For patients who met relapse criteria and were retreated with ixekizumab, only data up to the time of relapse will be included in the maintenance of effect analyses. These patients will be

considered non-responders to categorical assessments per the NRI imputation method (see Section 12.2.1.4.1).

Treatment comparisons of categorical efficacy variables will be made using a logistic regression analysis with treatment in the model. The proportions and 95% CI, the difference in proportions, and the 95% CI of the difference will be reported. Secondary analysis on the categorical efficacy variables may be conducted using a Fisher's exact test.

Treatment comparisons for continuous efficacy variables will be made using MMRM model. An ANCOVA model may also be used.

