**Proportion of Patients with sPGA (0, 1) at Week 60**

Treatment comparisons during maintenance dosing as described in Section 12.2.1.2 in the proportion of patients maintaining an sPGA (0, 1) from Week 12 (Visit 7) after re-randomization at start of Maintenance Dosing Period to Week 60 (Visit 19) will be analyzed using a logistic regression model defined in Section 12.2.1.2. Missing data will be imputed using the NRI method described in Section 12.2.1.4.1.

**Proportion of Patients with an Itch NRS  $\geq 4$  point reduction from baseline at Week 12 for patients who had a baseline Itch NRS  $\geq 4$** 

For patients who had a baseline Itch NRS  $\geq 4$ , the number and percentage of patients achieving an Itch NRS  $\geq 4$  point reduction from baseline at Week 12 (Visit 7) will be presented by treatment group. Treatment comparisons between each ixekizumab dose regimen and placebo in the proportion of patients achieving an Itch NRS  $\geq 4$  point reduction from baseline at Week 12 (Visit 7) will be analyzed using the logistic regression model defined in Section 12.2.1.1. Missing data will be imputed using the NRI method described in Section 12.2.1.4.1.

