6.1.3. General Considerations for Analyses during Period 3 (Maintenance Dosing Period)

Period 3 starts at the first injection of study treatment at Week 12 (Visit 7) and ends on the date of Week 60 (Visit 19) or the date of the ETV (if it occurs between Weeks 12 and 60).

For Period 3 efficacy and health outcomes analyses, baseline is defined as the last non-missing assessment recorded on or prior to the date of first injection of study treatment at Week 0 (Visit 2). In most cases, this will be the measure recorded at Week 0 (Visit 2).

Unless otherwise specified, for Period 3 safety analyses, baseline and baseline period are defined as the last non-missing assessment prior to the first injection of study treatment at Week 12 (Visit 7). In most cases, this will be the measure recorded at Week 12 (Visit 7). For treatment-emergent adverse events, baseline is the event started prior to the study drug injection at Week 12 (Visit 7) and continued into Period 3.

For patients who met relapse criteria (loss of response; sPGA ≥ 3) and were retreated with ixekizumab, only data up to the time of relapse will be included in the maintenance of effect analyses. These patients will be considered non-responders to categorical assessments per the NRI imputation method (see Section 6.2.1).

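### SAP 6.1.1 and SAP 6.1.3 / protocol 12.2.1.2 disagree on where Period 3 data stop at relapse and for which relapsers; keep the relapse visit and define *retreated*

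*SAP*

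**What the plan says.** Three sets of text govern data around relapse (sPGA of 3 or more) in Period 3.

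- **SAP 6.1.1**, defining the Maintenance Dosing Period Primary population: "Only information prior to relapse will be presented". There is no limit to particular relapsers or to particular kinds of data.
- **SAP 6.1.3**: "only data up to the time of relapse will be included in the maintenance of effect analyses", with these patients then treated as non-responders under NRI. The rule is confined to relapsers who were retreated. **Protocol 12.2.1.2** has the same scope: "For patients who met relapse criteria and were retreated with ixekizumab".
- **SAP 6.4 and 6.12.1.2.1** stop at the date of relapse for all relapsers, and **SAP 6.1.3.3** starts the re-treatment period at the relapse visit.

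On who is retreated, protocol 7.1.3 switches placebo relapsers to ixekizumab, while those already on ixekizumab "will continue on 80 mg ixekizumab Q4W in order to maintain the study blind and to evaluate the long term efficacy of ixekizumab treatment". The retreatment objective in protocol 6.2.2 concerns efficacy "following disease relapse after re-randomization to placebo treatment in the Maintenance Dosing Period". On the other side, the Relapse population (SAP 6.1.1, Table RHBH.6.1) includes both ixekizumab/ixekizumab groups, and SAP 6.12.1.2.2 computes re-treatment exposure for that whole population.

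**The concern.** There are two separate gaps.

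**Boundary.** If the cut falls before relapse, the visit that shows the relapse is lost. That visit carries the worst pre-switch values. Rebound after withdrawal is a stated objective, and one of its three criteria depends on sPGA at such a visit. The continuous Period 3 models would also lose those values. Most are expected on placebo, so the differences would tend to shrink.

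**Scope.** Take an ixekizumab/ixekizumab relapser who is back at sPGA 0 or 1 by Week 60. Under 6.1.1 the Week 60 value is cut, is missing, and becomes a non-response by NRI. Under 6.1.3, if continuing is not retreatment, the value stays and counts as a response. The estimates for gated Tests 6 and 7 could therefore differ between two programmers working from the same data.

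Two related gaps follow. SAP 6.2.2 defines LOCF only for patients who discontinue, which relapsers do not. Table RHBH.6.5 lists the categorical MMRM without NRI, so it is unclear whether relapsers enter it as non-responders or as missing.

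**Working it through.** **1. Planned figures (SAP 5.3).** Per induction regimen, 168 × 0.70 = 117.6 patients are re-randomised; split 2:1 this gives 78 and 39. The plan states power above 99%, "assuming the proportions of patients maintaining sPGA (0, 1) are 70% for 80 mg Q4W and 10% for placebo", with two-sided Fisher at 0.025. Exact enumeration gives 0.999999, so the stated figure reproduces.

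**2. Rebound by sPGA.** Inclusion criterion [4] ("Have both an sPGA score of" at least 3) sets the baseline floor, and SAP 6.1.3 fixes the efficacy baseline at Week 0.

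| Baseline sPGA | Scores above baseline | Is each a relapse (3 or more)? |
|---|---|---|
| 3 | 4, 5 | yes |
| 4 | 5 | yes |
| 5 | none | not applicable |

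Strictly pre-relapse scores are 0, 1 or 2, and none exceeds any baseline. The sPGA count is always zero under 6.1.1 as written, and can be met once the relapse visit is kept. The PASI and phenotype criteria are not tied to sPGA in this way.

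**3. Placebo values exposed to the boundary.** Every placebo relapser is a Week 60 non-responder. At the planned 10% response, at most 0.90 × 39 = 35.1, about 35 of 39 per regimen, could lose a relapse-visit value. The effect on the MMRM or LOCF difference cannot be computed from the documents.

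**4. Scope, per patient.** One ixekizumab/ixekizumab patient changing Week 60 status moves that arm by 1/78 = 1.28 points. The placebo arm is the same under either rule.

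**5. Scope, total.** The documents give neither the relapse rate on ixekizumab nor the share back at sPGA 0 or 1 at Week 60. As an assumption only, take 5–30% relapse and 10–50% recovery:
- low: 78 × 0.05 × 0.10 = 0.4 patients, 0.5 points
- high: 78 × 0.30 × 0.50 = 11.7 patients, 15 points

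A 75% recovery rate is not credible beside the planned 70%. With 30% relapse, the shift would be 22.5 points, leaving 47.5/70 = 68% response in non-relapsers against 75% in relapsers.

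**6. Test 6 conclusion.** Planned counts are 0.70 × 78 ≈ 55 and 0.10 × 39 ≈ 4. Two-sided Fisher against 4/39:

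| Ixekizumab responders of 78 | p |
|---|---|
| 55 | 2.7e-10 |
| 43 | 2.3e-6 |
| 23 | 0.0210 |
| 22 | 0.0337 |

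Significance at 0.025 is lost only at 22, that is after 55 − 22 = 33 changes. Fisher is the planning test; the planned analysis is logistic regression. Test 7 has no planning rate, so it is not computed.

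**The case against.** **The strict cut cannot be meant.** SAP 6.1.3.1 dates time to relapse by the first sPGA of 3 or more in this same population, and SAP 6.13.2.2 summarises its relapse rate. Both need the relapse visit. This stands: the 6.1.1 wording is probably unintended. A reader might infer that the plan cannot detect rebound at all. The documents do not support that, given these analyses and the two other rebound criteria.

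**The SAP's own usage settles scope.** It applies the word re-treatment to a Relapse population that includes ixekizumab/ixekizumab patients. On that usage every relapser is cut and is a non-responder, and the passages agree. This carries weight, and the SAP leans that way. It does not close the matter, because protocol 7.1.3 and the retreatment objective in 6.2.2 point the other way, and no definition is given.

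**Maintaining response from Week 12 to Week 60 could mean never losing it**, so relapsers would fail under either rule. That is possible. But the protocol heads the analysis "Proportion of Patients with sPGA (0, 1) at Week 60", SAP 6.2.1 judges response at the analysis time point, and Test 7 also counts patients who newly achieve sPGA 0.

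**The 6.1.1 sentence does useful work for safety.** It is the explicit text keeping post-switch ixekizumab adverse events out of the Primary-population placebo columns, while exposure stops at relapse. This is correct, and the fix must preserve it.

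**Conclusion.** The passages conflict in current text and should be aligned. As written, SAP 6.1.1 makes the sPGA rebound criterion impossible to meet and removes relapse-visit values from the Period 3 continuous analyses. The first result is purely logical and needs no assumption; the size of the second is unknown.

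The scope question is an undefined term with evidence on both sides. Its size is 1.3 points per affected patient in an arm of 78, and the total is not derivable from the documents.

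A reader might go further and conclude that Test 6 is at risk, or that the maintenance rate could be off by more than 20 points. Neither is supported: at the planning rates about 33 of 55 responders would have to change status, and the largest shifts need relapsers to respond better than non-relapsers. What is at stake is the estimates and the rebound count, not the expected test result.

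**What to change.** 1. **SAP 6.1.1:** state that efficacy and health outcome data up to and including the relapse visit are used for all relapsers in the Primary population. Keep the present restriction for safety and exposure, with data after the first post-relapse dose belonging to the Relapse population, in line with 6.1.3.3, 6.12.1.2.1 and 6.12.1.2.2.
2. **SAP 6.1.3:** define *retreated*, saying whether it covers ixekizumab/ixekizumab relapsers who continue, and reconcile it with 6.1.1 and protocol 12.2.1.2. Apply one rule to relapsers in both arms in the NRI, categorical MMRM, MMRM and LOCF analyses. Report how many ixekizumab/ixekizumab patients have a Week 60 status that depends on the rule. Document any departure from the protocol as SAP 6.1 requires.
3. **SAP 6.9.4.2.1:** state that the rebound count includes the relapse visit.

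The cost is a few sentences, minor programming and one extra count. sPGA and PASI are already scheduled at every Period 3 visit. Keeping the relapse visit does not remove all bias from the MMRM, because later values for relapsers remain cut.
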